**A COMPARATIVE STUDY BETWEEN THE DIFFERENT
LEVELS OF TEMPOROMANDIBULAR JOINT ARTHROSCOPY
IN THE MANAGEMENT OF TMJ INTERNAL DERANGEMENT
(A RANDOMIZED CLINICAL TRIAL)**

02/02/2022

ABSTRACT

Introduction: Temporomandibular disorders (TMD) are common conditions with an estimated prevalence rate of 5 to 12% of populations, whereas only 3 to 4% of patients get suitable treatment. Nowadays, minimally invasive arthroscopy has eliminated the use of many of the more complex surgical procedures. Numerous intra-articular operative arthroscopic techniques have been reported in the literature since the advent of temporomandibular joint (TMJ) arthroscopy. However, randomized controlled trials regarding outcomes are lacking nor are there strong evidence supporting one operative technique over another.

Aim: to compare the three levels of TMJ arthroscopy in the management of temporomandibular joint internal derangement to develop standardized patient selection criteria and treatment options to be used by all investigators.

Subjects: The study will be conducted on 30 patients with TMJ internal derangement (**Wilkes III**). Patients will be randomized into three groups:

Group I: 10 patients will be treated with level (I) arthroscopy (Lysis and lavage).

Group II: 10 patients will be treated with level (II) arthroscopy (operative arthroscopy).

Group III: 10 patients will be treated with level (III) arthroscopy (operative arthroscopy + disc repositioning and fixation)

Methods: All patients will be assessed clinically and radiologically by using MRI preoperatively to assess disc position. Then patients will be operated on randomly by either level. Then follow-up will be done for all patients for 6 months.

Results: Results will be tabulated and statistically analyzed.

Keywords: TMJ arthroscopy, Internal derangement, Wilkes III, Arthroscopy levels, Arthroscopic discopexy, operative arthroscopy, Lysis and lavage.

INTRODUCTION

The temporomandibular joint (TMJ) is the only diarthrodial articulation of the human joints. It is known as ginglymo-arthrodial joint and is formed by the bony articulations of the mandibular condyle with the glenoid fossa of the temporal bone. Interposed between the condyle and the fossa is a piece of dense avascular fibrous connective tissue namely the TMJ disc. The disc divides the joint into superior and inferior compartments, which normally do not communicate with each other. The condyle and disc are in a normal anatomic relationship if the posterior band of the disc is located above the condylar head when the mandibular condyle is centrally positioned in the fossa.⁽¹⁾

The prevalence of temporomandibular disorders (TMD) is thought to be greater than 5% of the population.⁽²⁾ Lipton and colleagues⁽³⁾ showed that about 6% to 12% of the population experience clinical symptoms of TMD. Patients with TMD symptoms present over a broad age range; however, there is a peak occurrence between 20 and 40 years of age.⁽⁴⁾ TMD symptoms are more prevalent in women than men. Women tend to develop TMD during their premenopausal years. The reasons behind the sexual disequilibrium in TMD prevalence are not entirely clear, but some have suggested a hormonal influence.⁽⁵⁻⁷⁾

Temporomandibular disorders (TMD) are a broad group of clinical problems involving the masticatory musculature, the temporomandibular joint, surrounding bony and soft tissue components, and combinations of these problems. Temporomandibular disorder (TMD) can result from any defect of one or both. Any problem that prevents this composite system of muscles, bones and joints from working in harmony may result in this disorder. Symptoms may be unilateral or bilateral and involve the face, head or jaw. The American Academy of Orofacial Pain (AAOP) classification divides TMD broadly into muscle related TMD (myogenous), and joint-related TMD (arthrogenous). The two types can be present at the same time, making diagnosis and treatment more challenging.⁽⁸⁾

The etiology of temporomandibular disorders is multifactorial. It includes trauma (such as traumatic injuries from eating, wide jaw opening, and dental management), bruxism (refers to a non-functional grinding and clenching of the teeth), malocclusion (causes inappropriate pressure on the joint), Stress and psychiatric illness. TMD is clinically characterized by pain in the temporomandibular region or in the muscles of mastication, pain radiating behind the eyes, in the face, shoulder, neck and/or the back, headaches, ear-ache or tinnitus, jaw clicking, locking or deviation, limited jaw opening, clenching or grinding of the teeth, dizziness and sensitivity of the teeth lacking oral disease. Pain is the most frequent symptom for

which patients seek medical attention.⁽⁸⁾

Internal derangement of the temporomandibular joint (TMJ) is one of the most common temporomandibular disorders. In 1983, Dolwick⁽⁹⁾ defined it as an abnormal relation between the temporomandibular disc with respect to the mandibular condyle, the temporal fossa, and the temporal eminence of the TMJ. Anterior disc displacement, with or without reduction, perforation of the retrodiscal tissue or the articular disc, and degenerative changes of the disc and/or the joint surfaces, may be present. Clinically, it may be accompanied by pain, limitation of mouth opening, clicking, and locking.⁽¹⁰⁾

In 1989, Wilkes⁽¹¹⁾ first established a classification to correlate clinical and radiological signs with surgical findings. The Wilkes classification consists of 5 stages based on clinical, radiologic, and intraoperative findings as follows:

Stage	Clinical Findings	Radiologic Findings	Surgical Findings
I	Painless clicking No locking No restricted motion	Slight anterior disk displacement that reduces on opening Normal osseous contours	Normal disk form Slight anterior disk displacement
II	Occasional painful clicking Intermittent locking Headaches	Slight anterior disk displacement that reduces on opening Early disk deformity Normal osseous contours	Thickened disk Anterior disk displacement
III	Frequent pain Joint tenderness Headaches Locking Restricted motion	Anterior disk displacement that does not reduce on opening Moderate disk deformity Normal osseous contours	Disk deformed and displaced Variable adhesions No bone changes
IV	Chronic pain Headaches Restricted motion with crepitus	Anterior disk displacement that does not recapture on opening Marked disk deformity Degenerative osseous changes	Disk perforation, displacement, and adhesions Degenerative changes in condyle and/or fossa
V	Variable pain Joint crepitus	Anterior disk displacement that does not recapture on opening Marked disk deformity Degenerative osseous changes	Disk perforation, displacement, and adhesions Degenerative changes in condyle and/or fossa

Diagnosing TMD requires a focused history and physical examination. Pain and limited range of motion are accepted symptoms of TMJ dysfunction. In general, patients with true intra-articular pathology have pain that is localized to the involved TMJ, which is increased with mandibular movement or masticatory function. Failure to reproduce pain localized directly to the involved TMJ, stimulated with masticatory load and/or movement, is a warning that the main cause of pain may not be intra-articular, even with magnetic resonance imaging (MRI) confirmed disc displacement. ⁽¹²⁾ Radiographic studies can also be used as supplemental diagnostic tools. Periapical radiographs can be used to rule out dental pathologies as a cause of referred pain. Cone beam computed tomography scans and panoramic radiographs will provide detailed imaging of the joint's bony structures but not the articular disk. MRI is the modality of choice for examining the disk position and morphology (gold standard). MRI may also show degenerative bony changes. MRI findings should not alone dictate treatment strategies. One must combine patients' clinical presentation, signs, and symptoms along with TMJ imaging when developing a treatment plan. The surgeon must treat the patient, not the MRI. Studies have revealed MRIs in asymptomatic subjects demonstrate disc displacement in the range of 32-38%.⁽¹²⁾ On MRI, joint effusions are radiographic signs of inflammation and an important finding in true intra-articular pathology.⁽¹³⁾ Inflammation indicates a transition from adaptive to pathologic changes within the joint. The MRI diagnosis of

anterior disk displacement uses the most superior aspect of the condyle (12 o'clock position) as a reference point. Anterior disk displacement is defined radiographically when the posterior disk tissue is located anterior to the 12-o'clock condylar position. Disk displacement may occur in asymptomatic patients such that all radiographic findings must be placed in clinical context before beginning TMJ treatments.⁽¹⁴⁾

Diagnostic arthroscopy provides the most important information determining the intra-articular surgery to be performed. Arthroscopic diagnosis is based on visual inspection of the pathologic intra-articular tissues. The most common intra-articular pathologies are synovitis, adhesions, osteoarthritis, anterior disc position, disc perforation and inflamed synovial plicae. Less common intra-articular pathologies include synovial chondromatosis, pigmented villonodular synovitis, crystalline arthropathies and neoplasia.⁽¹⁵⁾

Different methods have been proposed to treat this entity, beginning with conservative approaches. Occlusal splint therapy, medical treatment based on nonsteroidal anti-inflammatory drugs (NSAIDs) and muscle relaxants, and physical treatment are the most common options among conservative methods. Those refractory cases in which no effective improvement in terms of pain and mandibular function is obtained are amenable to further surgical treatment.⁽¹⁶⁾

Initially, surgical treatment for an internal derangement generally consisted of a discectomy, regardless of the type of internal derangement that was present.⁽¹⁷⁾ However, in 1979, Farrar and McCarty⁽¹⁸⁾ described surgical repositioning of the disc (discoplasty), showing that it was not necessary to remove the disc in most instances. Nevertheless, there were still instances where removal of the disc was necessary, because large, irreparable perforations, malformation of the disc, or calcification of the disc made it impossible to perform a discoplasty.⁽¹⁹⁾

During the period when most surgeons were performing open surgical procedures for internal derangements of the TMJ, a small group of surgeons was beginning to experiment with arthroscopic surgery. First introduced by Ohnishi in 1975, this modality opened a new era in the diagnosis and treatment of such conditions.⁽²⁰⁾

Initially, arthroscopic treatment of patients with an internal derangement consisted mainly of lavage of the joint to remove tissue breakdown products and inflammatory cytokines and the lysis of any adhesions that were present. Eventually, other intra-articular surgical manipulations such as mechanical debridement, lateral capsular release, and disc repositioning and fixation by suturing or by electrocauterization, lasering, or sclerosis of the retrodiscal tissue were added.⁽¹⁹⁾

Surgeons have described three levels of TMJ arthroscopy, Level I the

most basic, involving arthroscopic lysis and lavage (L&L) with diagnostic evaluation, Level II (operative arthroscopy) involves arthroscopic lysis, lavage, needle working instrument used for operative maneuvers including visualized lysis of adhesions or targeted-tissue medication injections, lateral pterygoid myotomy or botulinum toxin injection and retrodiscal coagulation. Level III includes more advanced procedures, double punctures, triangulation and visualized intraoperative maneuvers, including removal of pathology, debridement, motorized shaving, synovial biopsies, disc mobilization or disc repositioning with stabilization (discopexy) either by sutures or a resorbable pin.⁽¹⁵⁾

According to Al-Moraissi et al, on the hierarchy of different treatments for arthrogenous TMDs, they concluded that there is new evidence that minimally invasive procedures are significantly more effective than conservative treatments for both pain reduction and improvement of maximal interincisal opening (MIO). In contrast to traditional concepts mandating exhaustion of conservative treatment options, minimally invasive procedures, therefore, deserve to be implemented rather early, i.e., as soon as patients do not show a clear benefit from an initial conservative treatment.⁽²¹⁾

According to Santana Santos et al, comparing the effectiveness of open discopexy versus arthroscopic techniques, the available evidence showed an overall decrease in pain score and an improvement in mouth

opening after TMJ surgeries with discopexy. Changes in the (MIO) were greater after arthroscopic disk repositioning compared to the open-joint procedure.⁽²²⁾

Nowadays, minimally invasive surgery has become the 1st choice as it is a quick procedure, less postoperative complications, short hospital stay, early rehabilitation, and return to work.⁽²³⁾

According to Murakami on the rationale of arthroscopic surgery of the TMJ, he stated that, although various arthroscopic disc repositioning and suturing techniques were reported, the success rate was comparable to arthroscopic lysis and lavage, and the documentation by postoperative imaging was insufficient.⁽²⁴⁾

According to Israel: Numerous intra-articular operative arthroscopic techniques have been reported in the literature since the advent of temporomandibular joint (TMJ) arthroscopy. However, Ideal randomized controlled trials regarding outcomes are lacking nor are their strong evidence supporting one operative technique over another.⁽¹⁵⁾

Nowadays, minimally invasive procedures have eliminated the use of many of the more complex surgical procedures. Despite such advancements, however, clinicians are still encountering some difficulty in successfully treating many of these patients and finding the answers to these problems will

depend on future developments.

A review of the literature reveals that there is lack of randomized clinical trials to compare between the three levels of TMJ arthroscopy in the management of TMJ internal derangement.

The null hypothesis states that there will be no significant difference between the three levels of TMJ arthroscopy. Consequently, by doing the necessary studies and comparing the results, we can accept or reject this theory to finally develop guidelines and standardized patient selection criteria that can be followed by all researchers.

AIM OF THE STUDY

To compare between the three levels of TMJ arthroscopy in the management of TMJ internal derangement in the following points:

Primary aims are to assess:

1. Pain score using the visual analog score (VAS).⁽²⁵⁾
2. Presence or absence of clicking.
3. Mouth opening measuring the maximal interincisal opening in MIS.
4. Lateral excursion movement.
5. Protrusive movement.

[figure not shown]
Secondary aims are to assess:

1. Operative time.
2. Post operative MRI (disc position).

CONSORT

TRANSPARENT REPORTING of TRIALS

Study design

This study will be a randomized controlled clinical trial, with 1:1:1 ratio and will be reported according to CONSORT guidelines ⁽²⁶⁾

PICO Question

Do patients with TMJ internal derangement treated with arthroscopy level I compared to arthroscopy level II or arthroscopy level III show better maximal interincisal opening and less pain?

Settings and Location:

Participants will be selected from the Maxillofacial and Plastic Surgery Department, Faculty of Dentistry, Alexandria University, Egypt.

Sample size calculation

The size was estimated based on 5% alpha error and 80% study power. The mean (SD) improvement in Maximum Interincisal Opening (MIO) after 6 months compared to the preoperative measurements was 6.09 (7.05) mm for Level I arthroscopy, (10) 6.7 (5.25) mm for Level II arthroscopy, ⁽²⁷⁾ and 18.5 (2.1) mm for Level III arthroscopy. ⁽²⁸⁾ Based on difference between independent means using F test and pooled SD = 4.8 mm, the minimum sample size was calculated to be 9 joints per group, increased to 10 joints to make up for lost to follow up cases. Total sample = number per group x number of groups = 10 x 3 = 30 joints. Sample size was based on Rosner's method ⁽²⁹⁾ calculated by G*Power 3.1.9.7. ⁽³⁰⁾

Randomization

Participants will be randomly assigned using online program (www.random.org) in order to allocate participants to the group.

Allocation Concealment

Sequentially numbered opaque sealed envelopes will be used to conceal allocation. One set of envelopes will be created to guarantee they were opaque, sealed and sequentially numbered.

Blinding

The patients will be blinded to the treatment group.

Intervention

Group I: 10 patients will be treated with level (I) arthroscopy (Lysis and lavage).

Group II: 10 patients will be treated with level (II) arthroscopy (operative arthroscopy).

Group III: 10 patients will be treated with level (III) arthroscopy (operative arthroscopy + disc repositioning and fixation).

Eligibility Criteria

Inclusion criteria

The patients with TMJ internal derangement will be divided into 5 stages according to Wilkes Classification.⁽¹¹⁾ Only patients with stage III will be

included in this study.

Exclusion criteria

1. Medically unfit patients.
2. Patients with TMDs secondary to malocclusion.
3. Psychological instability.
4. Patients operated before for other TMJ problems.

Materials

In all procedures, 1.9 mm, 30-degree optical device, sleeves, sharp and blunt trocars, adhesion knives, an exploratory probe, a bipolar electrode (Karl Storz Endoscopy, Tuttlingen, Germany) and coblator.

A specific material for pin placement is A third custom-made cannula (2.7mmdiameter) with a distal parallel double window (10 _ 2 mm) for direct view control of pin fixation, a long 1.5-mm rotatory drill for perforating disc and condyle, and an impactor with hammer (fixation kit).

Resorbable pins are Smart Nail (ConMed, Linvatec, Tampere, Finland), 1.5mm _ 16mmsize (head of pin 2.5mm in diameter and flange of 1 mm) and manufactured of polylactic acid copolymer (Self-Reinforced 96L/4D PLA). The mean degradation period was standardized between 18 and 26 months. ⁽³¹⁾

Pre-surgical evaluation

All patients will be subjected to full history taking, full clinical examination and investigations including preoperative MRI and Panoramic x-ray to assess the dental condition.

Surgical technique

- 1- All procedures will be done under general anesthesia (nasotracheal intubation).**
- 2- The triple-channel arthroscopic technique of McCain et al is used⁽³²⁾**

After the first puncture of the fossa, a systematic diagnostic arthroscopy is carried out. A second puncture is carried out aiming at the anterior recess under direct arthroscopic visualization (Level I).

3- Anterior release: (*Level II*)

Through the working cannula additional local anesthesia is injected to avoid post-operative pain and to decrease bleeding; it can also reduce the risk of masticatory muscle nerve injury. A Knife, coblation or laser probe are used to cut the anterior attachment of the disc and the neighboring part of the lateral pterygoid muscle. The incision line is located approximately 2–3 mm anterior to the anterior band of the disc and is

carried out across the whole width from medial to lateral. The depth of the anterior release is no more than 2 mm to avoid breaking large blood vessels and damaging the masticatory muscle nerve in the anteromedial synovium.

5- Retrodiscal scarification or contracture

Retrodiscal tissue is contracted using bipolar cautery, laser, or coblation. The target area of the retrodiscal contracture is generally the boggy and redundant synovium found lateral to the oblique protuberance. Contracture is visible during the procedure, but the most significant contracture occurs 2 to 3 weeks postoperatively as the scar thickens. The purpose of the contracture is to enhance the posterior positioning of the disc and hold it there. The posterior synovectomy and the scar contracture are also done to reduce volume of the joint space so the disc can sit more posteriorly.

6- Disc reduction

After the anterior release is completed, the obturator is positioned at the anterior margin of the disc and the disc is pushed backwards. The obturator slides along the surface of the disc and arrives in the posterolateral recess. The retrodiscal tissue is pushed down inferiorly and posteriorly.

7- Disc fixation: (Level III)

A disc fixation can be accomplished in 1 of 2 ways. The first and more traditional way is the suture discopexy. A second way is by rigid fixation with either resorbable or titanium screws. Regardless of the methodology of fixation, the disc is held in reduction during the course of the fixation. The target area of fixation is the posterior lateral corner of the disc-condyle assembly, the area of the lateral pole where the disc attaches to the condyle.

Postoperative management

Antibiotics and nonsteroidal anti-inflammatory drugs are routinely prescribed for 5 days. The softness of the postoperative diet should be decreased slowly. Exercises to improve mouth opening are explained to the patient and start 1 week after operation.

In patients with significant postoperative occlusal changes, a splint is recommended. It is designed to raise the bite and prevent contact between upper and lower incisors and canines. Due to the resulting distalization of the bite force, joint loading is reduced, which contributes to the joint's rehabilitation. The appliance should be left in place around the clock during the first ten postoperative days, then used at night for four additional weeks.⁽³⁴⁾

Follow up

- Pain assessment using VAS (Visual Analogue Scale) ⁽²⁵⁾

- Clicking (improvement or persistence).
- Range of motion ⁽³³⁾ including: maximal interincisal opening, lateral excursion movement and Protrusive movement
- Post-operative MRI at 6 months for detection of disc position.
- All patients will be followed up at 1, 3, 6 months.

ETHICAL CONSIDERATIONS

Research Ethics Committee approval

The research protocol will be approved by the Research Ethics Committee of Alexandria University Faculty of Dentistry (IRB No. 001056 – IORG 0008839) prior to any research-related activities

All research activities involving human subjects will abide with the Declaration of Helsinki ⁽³⁴⁾ and other ethical guidelines adopted by the Research Ethics Committee of Alexandria University Faculty of Dentistry.

The benefits to the participant and/or the community

1. Treatment of patients with internal derangement with minimally invasive surgery (TMJ arthroscopy).
2. Short hospital stay with early recovery and rapid return to work.

The risks to the participant and/or the community

1. The need for long-term follow-up postoperative.
2. The exposure to radiation in MRI which is needed for follow-up at 6 months.

Anonymity and Confidentiality

The anonymity and confidentiality of the participants will be preserved by not revealing their names and identity in the data collection, analysis and reporting of the study findings.

The identity of participants will be kept confidential or anonymous and the assurances extend beyond protecting their names to also include the avoidance of using self-identifying statements and information.

DATA MANAGEMENT & STATISTICAL ANALYSIS

Data will be collected and analyzed statistically using ANOVA test to compare between the three groups.

REFERENCES

2. Thapliyal GK. Peterson's Principles of Oral & Maxillofacial Surgery. *Med J Armed Forces India.* 2006;62(1):89-.

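### Five unranked primary outcomes, no primary visit and no multiplicity rule under one accept-or-reject null hypothesis, with alpha and power set only for MIO change at 6 months

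*Combined protocol and SAP*

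**What the plan says.** The end of the INTRODUCTION sets one hypothesis: "The null hypothesis states that there will be no significant difference between the three levels of TMJ arthroscopy". It names no outcome and no visit. The text goes on to say that "we can accept or reject this theory to finally develop guidelines and standardized patient selection criteria", and the Abstract gives the aim as "to develop standardized patient selection criteria and treatment options to be used by all investigators".

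AIM OF THE STUDY reads "To compare between the three levels of TMJ arthroscopy in the management of TMJ internal derangement in the following points". Under "Primary aims are to assess" it lists five items without ranking: VAS pain, clicking (present or absent), MIO, lateral excursion and protrusion.

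The PICO Question is narrower. It asks whether patients "treated with arthroscopy level I compared to arthroscopy level II or arthroscopy level III show better maximal interincisal opening and less pain". It names no visit and does not rank the two outcomes.

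Sample size calculation is the only place with an error rate: "The size was estimated based on 5% alpha error and 80% study power". The quantity behind it is "improvement in Maximum Interincisal Opening (MIO) after 6 months compared to the preoperative measurements".

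Follow up schedules visits at 1, 3 and 6 months and ties only the MRI, a secondary aim, to 6 months. DATA MANAGEMENT & STATISTICAL ANALYSIS is one sentence saying that ANOVA will compare the three groups. It gives no test level, ranking, multiplicity rule or pairwise method.

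**The concern.** A single null hypothesis needs a rule for rejecting it. The plan does not say how many of the five outcomes must differ, at which visit, or how Level I is to be compared with Level II or III, which is what the PICO Question asks. The sections also point in different directions: the sample size leads with MIO, the aims list pain first, and the PICO Question pairs the two.

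Two things are at stake. If a difference on any one outcome is enough, the 5% in the sample size section does not describe the risk of wrongly concluding that the levels differ. Even if each outcome is read on its own, the one that carries the conclusion can be picked after the results are seen. The conclusion is meant to feed guidelines and selection criteria for other investigators.

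**Working it through.** **1. The plan's own figure.** Inputs from Sample size calculation: mean MIO gains of 6.09, 6.7 and 18.5 mm; SDs of 7.05, 5.25 and 2.1 mm; common SD 4.8 mm; F test; alpha 5%; power 80%.

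- Grand mean = (6.09 + 6.7 + 18.5)/3 = 10.43 mm. The SD of the three means (divisor 3) is 5.71 mm, so f = 5.71/4.8 = 1.19.
- Power comes from the noncentral F distribution with noncentrality f² × N. Three per group gives 69% and four gives 88%, so 80% power needs 4 per group. The stated 9 does not reproduce. At 9 per group, f² × N = 1.416 × 27 = 38.2 and power is 99.97%.
- 4.8 is the plain average of the three SDs; the root mean square is 5.22. Power at 9 per group is 99.9% with 5.22 and 95.2% with 7.05, the largest SD.

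MIO is therefore not short of patients on the plan's assumptions. The gap lies in the decision rule.

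**2. False-conclusion rate at one visit.** Two assumptions are needed that the plan does not state: each of the five outcomes is tested at 5%, and any one significant result rejects the null. If the outcomes are independent, the rate is 1 − 0.95⁵ = 22.6%. With correlated outcomes (simulated one-way ANOVAs, three groups of 9, no true differences):

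| Common correlation (assumed) | 0 | 0.3 | 0.5 | 0.7 | 0.8 | 0.9 |
|---|---|---|---|---|---|---|
| At least one p < 0.05 | 23% | 21% | 19% | 16% | 13% | 11% |

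- Follow up groups MIO, lateral excursion and protrusion as range of motion. If those three correlate at 0.8 to 0.9 and all other pairs at 0.3 to 0.5 (assumed), the rate is 16% to 18%.
- With clicking simulated as yes/no at an assumed prevalence of 10% to 50%, and correlation from 0.9 down to 0, it is 12% to 23%.
- Testing all three visits would raise it further. The plan does not say it will do so, and no figure is claimed.

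**3. Does the proposed order hold 5%?** In the single-primary order:

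- If the overall MIO null is true, every false claim requires a false overall MIO rejection, which has probability 5%.
- If it is false, at most one of the three pairwise MIO nulls can be true, because two would make all three means equal. That contributes at most 2.5%. The pain branch adds at most 2.5% by the same argument. The total is at most 5%.

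Simulation with Welch tests (several null patterns; MIO–pain correlations 0, 0.5 and 0.9; MIO SDs equal or as stated) gives about 3.4% to 5.3%, both for this order and for the Holm alternative. The slight excess is simulation error and Welch's approximation at 9 per group. Looser variants fail:

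- pairwise MIO tests and pain both at 5%: up to 9.6%;
- Holm with pairwise tests in any significant outcome: up to 7.4%;
- ordinary F and pooled-SD t-tests with the stated SDs: up to 8.5%.

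**4. Power for MIO under the proposed order** (Welch, 9 per group, the plan's means; pairwise tests follow a significant overall test at 5%):

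| Common SD | Overall, 5% | Overall, 2.5% | I vs III, 2.5% | II vs III, 2.5% | I vs II, 2.5% |
|---|---|---|---|---|---|
| 4.8 | 99.9% | 99.8% | 99.7% | 99.4% | 3% |
| 5.22 | 99.8% | 99.2% | 99% | 98% | 3% |
| 7.05 | 93% | 87% | 87% | 83% | 3% |

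Level I against II is near zero because the plan expects only 6.7 − 6.09 = 0.61 mm between them. No testing order changes that.

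**The case against.** **The aims can be read as five separate comparisons.** This is a fair reading of the aims section. Each test then keeps its own 5% and the 11% to 23% does not apply. What remains is that the outcome and visit behind the single accept-or-reject conclusion are not named.

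**A lead outcome is implied.** The sample size section uses MIO change at 6 months, and its F test matches the ANOVA sentence. That is a strong hint, but no section designates MIO, and the aims and PICO Question point elsewhere.

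**The error rates assume no difference on any outcome.** If the plan is right about MIO, rejecting the null is correct, and the realistic risk is a false claim about another outcome or pair. This stands as a limit on the figures. The complete null is still possible, because the three MIO means come from three separate cited studies.

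**A lighter remedy exists.** Bonferroni at 1% for each of five outcomes at 6 months keeps every primary aim. Ordinary-F power for MIO at 9 per group is then 99.6%, 98.7% or 82% at SD 4.8, 5.22 or 7.05; with Welch it is about 99%, 97% or 76%. This is a legitimate option. It drops below 80% with Welch at the largest SD, still needs a pairwise rule, and spreads alpha over four outcomes whose power cannot be computed.

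**Pain is listed first and is half of the PICO Question.** Placing it behind MIO is a choice for the sponsor, so the fix offers a co-primary alternative.

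**Conclusion.** The concern holds. As written, the plan neither fixes which outcome and visit decide the trial nor holds that decision to the stated 5%. The first part rests on the text alone. The size of the second, roughly two to four and a half times 5% at one visit, depends on two unstated rules (each outcome tested at 5%, any one sufficient) and on correlations the documents do not give. The design and sample size need not change on this account; the decision rule should be written down before outcome data are seen.

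**What to change.** In AIM OF THE STUDY and DATA MANAGEMENT & STATISTICAL ANALYSIS, adopt one of two rules, and date it before any outcome data are examined, since only patients are blinded.

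**Single primary (preferred, because it matches the sample size).** Name MIO change from preoperative to 6 months as the primary outcome and test it across the three levels at 5%. Only if it is significant:

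1. test the three pairwise MIO differences at 2.5% each;
2. test VAS pain at 6 months across the levels at 2.5% and, if significant, its pairwise differences at 2.5% each.

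**Co-primary.** Apply Holm to MIO and VAS pain at 6 months: the smaller p-value at 2.5% and, only if it is significant, the other at 5%. Run pairwise tests at 2.5% each only if both are significant.

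Under either rule:

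- State whether pain is the 6-month value or the change from preoperative.
- Use Welch ANOVA and Welch t-tests, since the planning SDs run from 2.1 to 7.05 mm. At SD 7.05 this lowers overall MIO power only from 95% to 93%.
- Make clicking, lateral excursion, protrusion and the 1- and 3-month values secondary, with 95% confidence intervals. Clicking should be analysed as a proportion.

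**Cost.** Some relabelling and a short paragraph; no extra patients or data. Four outcomes (single primary) or three (Holm) lose primary status. With a single primary, pain has no confirmatory test if MIO is not significant, and is otherwise tested at 2.5%. With Holm, there is no confirmatory pairwise answer unless both outcomes are significant. Power for pain cannot be computed, because the documents give no effect size or SD for it.
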